#### 10.2.4 Suspected unexpected serious adverse reactions (SUSARs)

Adverse reactions are all untoward and unintended responses to an investigational product related to any dose administered.

Unexpected adverse reactions are SUSARs if the following three conditions are met:

1. the event must be serious (see chapter 9.2.2);

2. there must be a certain degree of probability that the event is a harmful and an undesirable reaction to the medicinal product under investigation, regardless of the administered dose;
3. the adverse reaction must be unexpected, that is to say, the nature and severity of the adverse reaction are not in agreement with the product information as recorded in:
  - Summary of Product Characteristics (SPC) for an authorised medicinal product;
  - Investigator's Brochure (IB) for an unauthorised medicinal product.

The sponsor will report expedited the following SUSARs through the web portal *ToetsingOnline* to the METC:

- SUSARs that have arisen in the clinical trial that was assessed by the METC;
- SUSARs that have arisen in other clinical trials of the same sponsor and with the same medicinal product, and that could have consequences for the safety of the subjects involved in the clinical trial that was assessed by the METC.

The remaining SUSARs are recorded in an overview list (line-listing) that will be submitted once every half year to the METC. This line-listing provides an overview of all SUSARs from the study medicine, accompanied by a brief report highlighting the main points of concern.

The expedited reporting of SUSARs through the web portal *ToetsingOnline* is sufficient as notification to the competent authority.

The sponsor will report expedited all SUSARs to the competent authorities in other Member States, according to the requirements of the Member States.

The expedited reporting will occur not later than 15 days after the sponsor has first knowledge of the adverse reactions. For fatal or life threatening cases the term will be maximal 7 days for a preliminary report with another 8 days for completion of the report.

The principal investigator (PI) is responsible for reporting SUSAR's. All coordinating investigators of subcenters should inform the principal investigator as soon as possible. All SUSAR's are reported unblinded to the competent authorities.

### 10.3 Annual safety report

In addition to the expedited reporting of SUSARs, the sponsor will submit, once a year throughout the clinical trial, a safety report to the accredited METC, competent authority, and competent authorities of the concerned Member States.

This safety report consists of:

- a list of all suspected (unexpected or expected) serious adverse reactions, along with an aggregated summary table of all reported serious adverse reactions, ordered by organ system, per study;
- a report concerning the safety of the subjects, consisting of a complete safety analysis and an evaluation of the balance between the efficacy and the harmfulness of the medicine under investigation.

### 10.4 Follow-up of adverse events

All AEs will be followed until they have abated, or until a stable situation has been reached. Depending on the event, follow up may require additional tests or medical procedures as indicated, and/or referral to the general physician or a medical specialist.

SAEs need to be reported till end of study within the Netherlands, as defined in the protocol

## 11. STATISTICAL ANALYSIS

This is an exploratory, feasibility study that serves to provide base case statistics for further prospective research. Primarily descriptive statistics will be used. Demographic and baseline characteristics will be summarized using means, standard deviations, medians, and ranges for continuous variables, and proportions for categorical variables. The PET results will be both qualitatively and quantitatively assessed in 15 patients. Categorical data will be assessed using the Fisher's exact test. Continual data (paired and unpaired) will be assessed using non-parametrical tests (i.e. Mann-Whitney U test and Kruskall-Wallis test).

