#### 5.4 Sample size calculation

The total sample size of the study is 15 patients at maximum. A maximum of 5 patients will participate in phase one and 10 patients will participate in phase two. With an expected accrual rate of 1-2 patients per month, the intervention part of the study could be completed within 12 months.

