#### 9.4.2 PET procedure and quantification of tracer uptake

[figure not shown]
[figure not shown]
In phase one, the tracer kinetics will be measured in order to determine the optimal tracer distribution time and to evaluate which simplified method is best suited for the quantitative analysis of the tracer uptake. For this purpose, 5 patients will undergo an extended PET acquisition protocol, both at baseline and after 6 weeks of treatment with immunotherapy. Immediately after injection of the tracer a dynamic PET scan will be acquired of the chest (single bed position; 60 minutes). The dynamic PET scan will be followed by two total body PET scans (head to toe; 12 bed positions, 3 minutes per bed position). The first total body PET starts at 60 minutes after tracer injection (i.e. immediately after the dynamic PET scan). After this scan (ca. 90-100 minutes after tracer injection), the patient can shortly leave the PET camera. An additional total body scan will be performed at 120 minutes after tracer injection. The two total body scans will be used to quantify tracer uptake in tumors and tumor contrast throughout the body in order to establish the optimal time point for imaging. If during this phase of the study either one of the two total body PET scans seems obsolete due to low tracer availability, small differences between both scans or whatever other reason, one scan will be omitted to minimize burden in the following patients.

In phase two, a single PET-scan will be performed at baseline and after six weeks of treatment at the optimal time point after tracer injection as determined in phase one. Both scans will be accompanied by a low-dose or diagnostic CT-scan for anatomic reference purposes. The scans will be performed one hour or two hours after tracer injection, depending on the optimal time of tracer injection as established in phase I.

Before the start of the imaging procedure, a venous catheter is placed in one arm and patients will be injected with approximately 200 MBq (0,63mL) [18F]PD-L1. Patients will be asked to drink 1 liter of water to promote the renal clearance of unbound tracer from the circulation in order to enhance signal to background ratio. Prior to scanning, patients will be asked to go to the toilet to empty their bladder in order to reduce the radiation burden to the patient and prevent high bladder uptake on the PET scan.

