**A.****B.**

\*Scan sequence will be determined based on phase one of this study

*Fig.2 – A: Detailed overview of the procedures in phase one of the study. Patients will be scanned both at baseline and after six weeks of treatment during a two hour scan protocol. B: Detailed overview of the procedures in phase two of the study. Again, patients will be scanned both at baseline and after six weeks of therapy. At both time points, only a single PET-scan will be performed. To assess PD-L1 expression by IHC a biopsy will be taken after both PET-scans.*

For quantification of tracer uptake, the investigator visually identifies tumor lesions on a PET or CT scan and determines a region-of-interest (ROI) around these lesions.  $[^{18}\text{F}]$ PD-L1-uptake in these ROI's will be corrected for body weight and injected dose and quantified as standardized uptake value

( $SUV_{max}$  and  $SUV_{mean}$ ). The absolute tracer uptake will be assessed both at baseline and six weeks after treatment initiation.

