#### 9.4.5 Biopsy

In phase two of the study at least one biopsy sample will be collected from an accessible tumor lesion after each PET scan. If possible, these tissue samples will be obtained from the same tumor lesions at baseline and after 6 weeks of treatment. Ideally biopsies will be taken from both [18F]PD-L1 PET positive as well as negative lesions within the same patient. Determination of the biopsy site will be based on tumor localization on previous diagnostic imaging studies and will be performed according to current safety criteria. A biopsy will be performed under local anesthetics and ultrasonographic or CT-guidance. Biopsy material will be FFPE.

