### 11.2 Secondary study parameter(s)

Heterogeneity between tracer uptake of separate tumor lesions will be determined. For this purpose the absolute difference in SUV between the two PET scans will be determined for all separate lesions and will be visualised in a table. Heterogeneity of this absolute difference in SUV will be analysed for

lesions in one patient (intra-patient heterogeneity) and for lesions between patients (inter-patient heterogeneity).

Although the study population is too small to generate statistical relevant information, the ability of PD-L1 expression to predict response to anti-PD1 treatment will be assessed as a secondary parameter. For this purpose the different lesions identified on the first PET-CT scan, will be qualitatively scored as responding (stable disease, partial or complete regression) or non-responding (progressive disease) according to the RECIST 1.1 criteria. The measured response will then be correlated to the absolute increase in SUV between the two PET scans for PD-L1 expression on PET and response will be correlated to the difference in immunohistochemical score for PD-L1 expression in tumor tissue samples.

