### 12.4 Benefits and risks assessment, group relatedness

Molecular imaging with a PET scan is an upcoming technique for obtaining non-invasive whole body information about specific molecular targets. In this imaging study we want to visualize PD-L1 expression in tumor lesions of patients with metastatic melanoma. This tumoral PD-L1 expression could serve as a predictor of response to anti-PD1 treatment. Results of this study could provide valuable information about the whole body distribution of PD-L1 in tumor lesions and heterogeneity in this distribution. In addition, this study will explore how intratumoral PD-L1 and PD1 expression is influenced by anti-PD1 treatment.

Patients will not benefit from participation in this study directly, but their participation helps to develop a new imaging technique which could provide more insights in PD-L1 expression in tumor lesions and predictive value of this PD-L1 expression.

Patients will be treated with anti-PD1 as part of their regular treatment or in the context of a clinical trial. So, this treatment will not cause any additional risk or burden to the patient in this imaging study. Patients will also get regular follow-up to assess disease control.

The tracer was well tolerated in pre-clinical toxicology studies performed in cynomolgus monkeys. For detailed information, we refer to the IB, version 1, 14 Dec 2015.

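### Section 11 sends paired continuous data to two tests for independent groups, and no paired test is named anywhere

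*Combined protocol and SAP*

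**What the plan says.** Section 11 gives one general rule for continuous variables: "Continual data (paired and unpaired) will be assessed using non-parametrical tests (i.e. Mann-Whitney U test and Kruskall-Wallis test". It names paired data explicitly, and the list after the abbreviation for 'that is' holds only those two tests. The same section calls the study exploratory and mainly descriptive.

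Paired values arise in several places:

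- **PET (section 9.4.2, below Fig. 2):** "The absolute tracer uptake will be assessed both at baseline and six weeks after treatment initiation". Section 11.1 adds that every lesion found at baseline is measured again at week 6.
- **IHC (section 9.4.5):** "If possible, these tissue samples will be obtained from the same tumor lesions at baseline and after 6 weeks of treatment".
- **Phase one (section 9.4.2):** each session includes total body scans at 60 and 120 minutes after injection. "The two total body scans will be used to quantify tracer uptake in tumors and tumor contrast throughout the body".

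Section 12.4 says that "this study will explore how intratumoral PD-L1 and PD1 expression is influenced by anti-PD1 treatment", which is a question about change within patients. On numbers, section 5.4 states: "A maximum of 5 patients will participate in phase one and 10 patients will participate in phase two".

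The other methods for continuous data are the Pearson or Spearman coefficient for PET against IHC (section 11.1) and the change analysis in section 11.2, where "the absolute difference in SUV between the two PET scans will be determined for all separate lesions and will be visualised in a table". That change is then related to response. Neither section names a test of whether the change differs from zero.

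**The concern.** Mann-Whitney U and Kruskal-Wallis compare separate groups of independent observations. If a patient's baseline value goes into one group and the same patient's week-6 value into the other, the test treats 10 patients as 20 unrelated ones. Variation between patients, which pairing would remove, stays in the comparison.

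An analyst who follows the sentence literally uses an unsuitable test. An analyst who departs from it chooses a replacement without a pre-specified rule, possibly after seeing the data. With at most 15 patients, two scan sessions each and mandatory biopsies in phase two, little information can be spared. The study is also meant to supply starting figures for later research.

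**Working it through.** **No figure to reproduce.** The document gives no alpha, effect size, SD or within-pair correlation, and the 15 patients are not derived from a calculation. The check therefore has a reading part and an illustrative part.

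**Reading.** No analysis passage names a signed-rank test, Friedman test, paired t-test or mixed model. Reading the abbreviation as a slip for 'for example' does not help, since a paired test is still not named.

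**Why the direction is conservative (one value per patient).** Let each visit have SD σ, let the within-pair correlation be ρ, and let there be n patients.

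- Variance of the mean difference assumed by an independent-groups test: 2σ²/n.
- Actual variance: 2σ²(1 − ρ)/n.
- Ratio of actual to assumed: 1 − ρ.

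A large-sample approximation to the rejection rate under no change, at nominal two-sided 0.05, is 2Φ(−1.96/√(1 − ρ)):

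- ρ = 0.3: 1.96/0.837 = 2.34, giving about 0.019
- ρ = 0.5: 1.96/0.707 = 2.77, giving about 0.006
- ρ = 0.7: 1.96/0.548 = 3.58, giving about 0.0004

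**Simulation.** Exact tests, 40,000 runs per cell, bivariate normal pairs, one pair per patient. The shift is in units of the between-patient SD at one visit. Assumed, not from the document: two-sided 0.05, the correlations, the shifts and normality. From section 5.4: 10 patients in phase two (the only phase with biopsies) and 15 in total, both ceilings on the number of pairs.

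Rejection rate at n = 10, signed-rank / Mann-Whitney:

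| Shift | ρ = 0 | ρ = 0.3 | ρ = 0.5 | ρ = 0.7 |
|---|---|---|---|---|
| None | 0.049 / 0.044 | 0.049 / 0.019 | 0.051 / 0.008 | 0.051 / 0.002 |
| 0.5 SD | 0.165 / 0.162 | 0.214 / 0.127 | 0.281 / 0.104 | 0.431 / 0.073 |
| 0.8 SD | 0.346 / 0.353 | 0.462 / 0.333 | 0.595 / 0.318 | 0.809 / 0.312 |
| 1.0 SD | 0.497 / 0.511 | 0.641 / 0.512 | 0.786 / 0.526 | 0.943 / 0.545 |

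The simulated Mann-Whitney rates under no change follow the approximation closely at ρ = 0.3 and in direction at higher ρ. A separate run of 10,000 replicates gave two-group Kruskal-Wallis rates under no change of 0.023, 0.010 and 0.004 at ρ = 0.3, 0.5 and 0.7, so the other named test behaves the same way.

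Power at a 0.8 SD shift for other numbers of pairs, signed-rank / Mann-Whitney:

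| Pairs | ρ = 0.3 | ρ = 0.5 | ρ = 0.7 |
|---|---|---|---|
| 15 | 0.661 / 0.530 | 0.798 / 0.534 | 0.952 / 0.558 |
| 8 | 0.320 / 0.285 | 0.434 / 0.270 | 0.640 / 0.252 |
| 6 | 0.177 / 0.176 | 0.242 / 0.163 | 0.376 / 0.140 |

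Log-normal values (log-SD 0.6 assumed) at n = 10, with a 0.8 SD shift on the log scale, give 0.436 / 0.334, 0.566 / 0.325 and 0.768 / 0.307.

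**Phase one.** The smallest two-sided signed-rank p-value with 5 pairs is 2/2⁵ = 0.0625, so a paired test there cannot reach 0.05.

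**Several lesions per patient.** SUV is recorded per lesion, so a paired test needs a unit of analysis. Simulating 15 patients with no change (10,000 runs, total variance 1), with 3, 5 or 8 lesions each, signed-rank on pooled lesions rejects 0.096, 0.159 and 0.231 when 10% of the variance is shared by a patient's lesions at a visit, and 0.160, 0.258 and 0.351 when 30% is. Signed-rank on patient medians stays at 0.045 to 0.052.

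**The case against.** The strongest reply is that no scheduled analysis depends on the sentence. Phase one reports dosimetry and scan timing, the phase-two primary analysis is a correlation, and section 11.2 takes within-lesion differences before relating them to response. Applying Mann-Whitney to those differences, responding against non-responding lesions, would keep the baseline to week-6 pairing. Section 12.4 is benefit and risk prose, not a planned test. All this is correct and limits the impact. It does not rescue the rule: section 11 chose to assign tests to paired data and assigned the wrong ones. For the response question, section 11.2 itself says: "Although the study population is too small to generate statistical relevant information".

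A second reply is that the authors plainly knew the paired/unpaired distinction, so the list may simply be incomplete. That is plausible, but the correction needed is the same.

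A third is that the power figures assume one value per patient, whereas the plan measures lesions. This stands as a limit on the illustration. With lesions pooled, Mann-Whitney need not be conservative. In a simulation of 10 patients with 3, 5 or 8 lesions each and no change (3,000 runs, assumed variance shares), it rejected 1.6%, 3.3% and 6.2% at a 10% patient-by-visit share, and 8%, 15% and 24% at 30%. This is an argument for fixing the unit of analysis, not for keeping the sentence. A mixed model would be another valid way to handle the clustering.

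Finally, the paired test does not always win. At zero correlation the two are level at n = 10. A run of 5,000 replicates at zero correlation favoured Mann-Whitney with fewer pairs (0.31 against 0.23 at n = 8; 0.21 against 0.14 at n = 6). Zero correlation is hard to expect for repeat measurements in the same patient, but the document gives no value.

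**Conclusion.** The concern holds. The sentence is wrong as written, not merely short on detail, and should be corrected.

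With one value per patient and positive correlation, the error makes a real change easier to miss and does not create excess false positives. At n = 10, a 0.8 SD shift and correlations from 0.3 to 0.7, the power lost runs from about 0.13 (0.462 − 0.333) to about 0.50 (0.809 − 0.312). The loss shrinks with fewer pairs and is absent at n = 6 with correlation 0.3. These sizes rest entirely on assumed alpha, correlation, shift and distribution.

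The practical weight is modest: no decision rests on a p-value, and the PET–IHC correlation, the table of SUV differences and the change-versus-response analysis are untouched.

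**What to change.** Replace the sentence in section 11 with wording such as:

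> Paired continuous data will be assessed using the Wilcoxon signed-rank test on one summary value per patient (e.g. the median SUV of lesions measured at both scans), with the median paired difference and its confidence interval. Unpaired continuous data will be assessed using the Mann-Whitney U or Kruskal-Wallis test. Paired comparisons in phase one (at most 5 patients) will be described only.

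The one-value-per-patient clause is needed because a signed-rank test on pooled lesions would itself reject too often when a patient's lesions change together. It applies only to this test. Lesion-level tables and the heterogeneity analysis in section 11.2 can stay as they are.

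The cost is one sentence of analysis wording, made before the data are analysed. No data collection, visit or procedure changes.

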### 11.1 Primary study parameter(s)

Tracer pharmacokinetics and the optimal time for scanning will be determined from the data obtained by the serial PET scans in first 5 patients. Output parameters are the radiation absorbed dose to major organs, the effective dose equivalent for patients, the recommended maximum injected dose for  $[^{18}\text{F}]$ PD-L1 and the optimal time point for scanning after tracer administration.

PD-L1 expression in melanoma tumor lesions will be quantified by measuring tracer uptake in tumor lesions. Tracer uptake will be corrected for body weight and injected dose and quantitatively assessed as standardised uptake value (SUVmean with associated standard deviation and SUVmax), which is calculated using the formula: [tissue activity concentration (MBq/g)]/[(injected dose (MBq)/body weight (g)]. SUV will be calculated for all predefined ROI's on the PET-CT scan at baseline. On the PET-CT scan at week 6 of treatment, SUV will be determined for all lesions detected at baseline as well as all newly detected tumor lesions.

Tumor uptake of  $[^{18}\text{F}]$ PD-L1 will be correlated with the amount of PD-L1 expression of melanoma cells and PD-1 and PD-L1 expression on tumor infiltrating immune cells in melanoma lesions. PD-L1 and PD1 expression will be measured by immunohistochemistry. Results of immunohistochemical staining will be described as a semi-quantitative score using the percentage of positive cells (continuous variable), intensity and pattern of staining (discrete variable). This semi-quantitative score will then be correlated to SUV of the corresponding lesion on the  $[^{18}\text{F}]$ PD-L1 PET. Correlation will be expressed as a Pearson/Spearman correlation coefficient depending on distribution of data. Results will be displayed in graphs.

### 11.2 Secondary study parameter(s)

Heterogeneity between tracer uptake of separate tumor lesions will be determined. For this purpose the absolute difference in SUV between the two PET scans will be determined for all separate lesions and will be visualised in a table. Heterogeneity of this absolute difference in SUV will be analysed for

lesions in one patient (intra-patient heterogeneity) and for lesions between patients (inter-patient heterogeneity).

Although the study population is too small to generate statistical relevant information, the ability of PD-L1 expression to predict response to anti-PD1 treatment will be assessed as a secondary parameter. For this purpose the different lesions identified on the first PET-CT scan, will be qualitatively scored as responding (stable disease, partial or complete regression) or non-responding (progressive disease) according to the RECIST 1.1 criteria. The measured response will then be correlated to the absolute increase in SUV between the two PET scans for PD-L1 expression on PET and response will be correlated to the difference in immunohistochemical score for PD-L1 expression in tumor tissue samples.

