**Primary objectives:**

Phase one: To assess the dynamics and kinetics of  $[^{18}\text{F}]$ PD-L1 in human subjects to establish optimal scan schedule.

Phase two: To validate the  $[^{18}\text{F}]$ PD-L1 PET tracer by association of PD-L1 tumor expression as determined on PET and PD-L1 expression as determined by immunohistochemistry and to assess the association between the radiological response to anti-PD1 treatment and PD-L1 expression as measured by PET scanning and by immunohistochemistry

**Secondary objectives:** To determine between-subject and within-subject variability in  $[^{18}\text{F}]$ PD-L1 uptake in melanoma and non-small cell lung cancer metastases

**Study design:** This is a feasibility study for the use of  $[^{18}\text{F}]$ PD-L1 as a PET tracer that will be conducted in a single center. The study consists of two phases. The aim of phase one is to provide pharmacokinetic information on the tracer and to determine the optimal time point for imaging. In the second phase the main study objective will be assessed.

**Study population:** The study population consists of patients diagnosed with metastatic melanoma or non-small cell lung cancer that are eligible for treatment with nivolumab, a PD-1 blocking monoclonal antibody. Patients must be at least 18 years of age. In total, a maximum of 15 patients will be included.

**Intervention (if applicable):** The main intervention of this study is a  $[^{18}\text{F}]$ PD-L1 PET scan. In both phase one and phase two a scan sequence will be performed both at baseline and 6 weeks after initiation of nivolumab treatment. The PET scans will be combined with either a low dose or diagnostic CT scan of chest, abdomen and pelvis and a MRI of the brain. In phase two, a biopsy of at least one accessible lesion will be performed to analyze PD-L1 expression using immunohistochemical staining after each PET scan.

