### 3.2 Phase two

Primary Objective:

- To assess the association of PD-L1 expression as measured by PD-L1 tracer uptake on PET and PD-L1 expression as measured by immunohistochemical (IHC) staining for PD-L1 of corresponding tumor lesions.
- To correlate response to anti-PD1 treatment with differences in tumor PD-L1 and PD1 expression between baseline and after 6 weeks of treatment, as quantified by PET and IHC analysis.

Secondary objectives:

- To characterize between-subject and within-subject variability in accumulation of the [F]PD-L1 tracer in melanoma and NSCLC metastases.

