### 9.2 Secondary study parameters/endpoints

Heterogeneity of tracer uptake between separate tumor lesions will be determined both for separate lesions within one patient (intra-patient heterogeneity) and for lesions in different patients (inter-patient heterogeneity).

Differences in PD-L1 expression, both assessed by PET scanning and IHC, between baseline and after 6 weeks of treatment with a PD1 immune checkpoint inhibitor will be correlated to response to treatment as measured by standard of care radiological response assessment.

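### Section 11.2 analyses the spread of the change in SUV between scans, but the secondary objective is the spread of tracer uptake itself

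*Combined protocol and SAP*

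**What the plan says.** The objective is worded as variability of a level. The summary has "To determine between-subject and within-subject variability in" tracer uptake, and section 3.2 has "To characterize between-subject and within-subject variability in accumulation of the" tracer. The matching endpoint in section 9.2 reads "Heterogeneity of tracer uptake between separate tumor lesions will be determined both for separate lesions within one patient (intra-patient heterogeneity", and it goes on to lesions in different patients.

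Section 9.2 puts the change over time in a separate paragraph, "Differences in PD-L1 expression, both assessed by PET scanning and IHC, between baseline and after 6 weeks of treatment", where it is to be correlated with response.

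The first paragraph of section 11.2 starts from heterogeneity of uptake between lesions and continues: "For this purpose the absolute difference in SUV between the two PET scans will be determined for all separate lesions". It then states "Heterogeneity of this absolute difference in SUV will be analysed for" lesions within one patient and lesions between patients. The second paragraph gives the change its own use: "The measured response will then be correlated to the absolute increase in SUV between the two PET scans for PD-L1 expression on PET".

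The levels themselves will be available. Section 9.4.2 says "The absolute tracer uptake will be assessed both at baseline and six weeks after treatment initiation", and section 11.1 plans SUV for the baseline lesions at both visits and for newly detected lesions at week 6.

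**The concern.** The aim stated at the start of 11.2 and the variable then analysed are different quantities. One is how unequal uptake is across lesions and patients at a given time. The other is how unequally uptake moves during six weeks of nivolumab. The change already has its place in the response analysis, while the uptake objective has no analysis of uptake specified for it.

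Section 11 presents the study as a source of starting figures for later research, and section 12.4 justifies it partly by what it may show about uneven PD-L1 distribution. A change SD reported as intra- or inter-patient heterogeneity could be taken by a later planner for variability of uptake.

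**Working it through.** **Inputs.** The documents give no SUV standard deviation, no correlation between visits and no measurement error, so there is no figure of the plan's to reproduce. All SUV values below are assumptions chosen to show the mechanism, without measurement error. SDs are sample SDs (n − 1).

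**Step 1: the relation.** Let s0 and s6 be the uptake SDs at baseline and week 6, and ρ their correlation. For a signed difference,

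Var(change) = s0² + s6² − 2ρ·s0·s6,

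plus measurement error. Only when s0 = s6 = s does this reduce to 2s²(1 − ρ), and equality cannot be presumed once treatment has started.

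**Step 2: one change SD fits many uptake SDs.**

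| s0 | s6 | ρ | Var(change) | SD(change) |
|---|---|---|---|---|
| 1 | 3 | 1/6 | 1 + 9 − 1 = 9 | 3.0 |
| 3 | 3 | 0.5 | 9 + 9 − 9 = 9 | 3.0 |
| 3 | 1.5 | 0.25 | 9 + 2.25 − 2.25 = 9 | 3.0 |
| 6 | 6 | 0.875 | 36 + 36 − 63 = 9 | 3.0 |

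A reported change SD of 3.0 therefore leaves the baseline uptake SD open between at least 1 and 6.

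**Step 3: within a patient, the order can reverse.**

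- Patient A: lesions at 2, 5, 8, 12 go to 3, 6, 9, 13. Uptake SD is 4.27 at both visits. The changes are 1, 1, 1, 1, so change SD is 0.
- Patient B: lesions at 5, 5, 5, 5 go to 3, 5, 7, 9. Uptake SD is 0, then 2.58. The changes are −2, 0, 2, 4, so change SD is 2.58. If the difference is taken without sign (2, 0, 2, 4), it is 1.63.

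A is the more heterogeneous at both visits. The 11.2 measure calls A homogeneous and B heterogeneous, signed or unsigned.

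**Step 4: the same happens between patients.** Patient means of 3, 6, 10 that all rise by 1 have uptake SD 3.51 and change SD 0. Means of 6, 6, 6 going to 4, 6, 8 have baseline SD 0 and change SD 2.00 (signed).

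**Step 5: the within/between split is not recovered either.** A simulation of 20,000 patients with five lesions each held the SDs of the change at 0.5 between and 0.5 within patients. It used three different (between, within) uptake SDs: (2, 1), (0.5, 3) and (0.5, 0.5). All three gave change components of about (0.5, 0.5).

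**Step 6: lesions new at week 6.** Section 11.1 plans only a week-6 SUV for these, so no difference exists. Take lesions at 4, 5, 6 that do not change, plus a new lesion at 12. Week-6 uptake SD is 3.59 with the new lesion and 1.00 without it. The change SD is 0.

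**The case against.** The strongest reply is that nothing is lost. SUV is collected for every lesion, section 11 promises mainly descriptive statistics, and section 9.2 and the first sentence of 11.2 commit to uptake heterogeneity, so a per-visit spread could be reported without breaching the plan. The aim is secondary and descriptive in a small feasibility study, no decision rule depends on it, and 11.2 openly names the difference as the thing analysed. This limits the weight of the point but does not remove it. Section 11 assigns means, SDs and ranges to demographic and baseline characteristics, and 11.2 is the only specific instruction for this objective.

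Three narrower replies:

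- Section 11.2 does not define which two scans it means, and phase one has two total body scans per session. Baseline versus week 6 is the natural reading, since the next paragraph uses the same phrase for the increase tied to response. On either reading the variable is a difference, not a level.
- The examples are constructed extremes. That is fair: they show what can happen, not what is likely here. Nor does the plan propose to rank patients; the reversal only shows that the measure does not track uptake heterogeneity.
- Section 11.2 has no explicit rule excluding new lesions. That is true, but without a planned baseline value they have no difference to enter.

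If heterogeneity of change was what the authors intended, then the objective, the endpoint and the opening of 11.2 are misworded, and the text needs reconciling all the same.

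**Conclusion.** The concern holds. As written, 11.2 answers a different question from the secondary objective, and its result identifies neither the size of uptake heterogeneity nor its division within and between patients. This conclusion rests on the wording of the sections and on the algebra, not on any assumed SUV value. The size of the distortion in this trial cannot be stated, because s0, s6, ρ and measurement error are all unknown.

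The consequence is moderate: a wrongly specified analysis variable for a secondary, descriptive aim in at most 15 patients, correctable with no loss of data. It should be corrected, because descriptive figures are this study's main product.

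**What to change.** Rewrite the first paragraph of 11.2 so that heterogeneity is described from SUV itself:

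- At baseline, give each patient's between-lesion SD and range, and the spread across patients of the patient means or medians.
- Repeat this separately at week 6, including newly detected lesions.
- Use one post-injection scan time for all patients when levels from the two phases are combined. For phase-one patients this is the total body scan at the time chosen for phase two.
- Keep the change in SUV as a separate summary of change under treatment, not labelled as uptake heterogeneity. Define it as baseline to week 6 and say whether it is signed.

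The cost is one paragraph of text and a few more descriptive tables from SUVs already planned in 9.4.2 and 11.1. No further scans, biopsies or patients are needed.
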